9.0 TREATMENT/INTERVENTION PLAN

9.1 Evaluation Prior to Initiation of Intervention

Prior to the initiation of each intervention session participant resting vital signs will be assessed as per **Appendix H** to ensure the participant can safely proceed with the session. The planned session will not be initiated if the exercise physiologist observes any concerns that may compromise participant safety and/or the integrity of the planned session.

9.2 Study Interventions

The study interventions are supervised linear aerobic training (Arm A), supervised nonlinear aerobic training (Arm B), or progressive stretching (attention control) (Arm C). All sessions will be performed in a supervised setting by an exercise physiologist. Sessions will take place at the Sidney Kimmel Center for Prostate and Urologic Cancers or Sillerman Center for Rehabilitation.

All aerobic training sessions will be prescribed by an exercise physiologist under the direction of the Program Director. All exercise physiologists are trained in either Basic or Advanced Cardiovascular Life Support (BLS/ACLS).

Participants will be instructed to adhere to fasting guidelines for food, caffeine, tobacco, alcohol and exercise as outlined in Appendix H.

All sessions, regardless of randomization arm, will include a warm-up. The aerobic arms, A and B, will also include a cool-down. Heart rate, oxygen saturation and blood pressure will be assessed prior to and following each intervention session. All adjustments to the intervention sessions will be implemented according to the standard care procedures of the exercise physiologists and will be source documented.

Aerobic Training Interventions (Arms A-C) (General Considerations)

The overall goal for all the exercise training groups will be 3 supervised exercise sessions per week an intensity between 50 to 100% of the individually determined $\text{v}_{\text{O}2\text{peak}}$ for aerobic training and an intensity between 50% to 85% of 1-RM for resistance training. All the exercise interventions are designed such that participants begin exercising at a low intensity (~50%-60% $\text{v}_{\text{O}2\text{peak}}$ / 1RM) that is subsequently increased to more moderate to vigorous intensity (~70%-100% $\text{v}_{\text{O}2\text{peak}}$ / ~70-85% 1RM) when appropriate. All interventions will be individually tailored to each patient following the principles of aerobic or resistance training prescription guidelines for adults.

9.2.1 Arm A -Aerobic Training

All aerobic training sessions will be performed on a cycle ergometers, targeting delivery of three cycling sessions/week at 55%-100% of $\text{v}_{\text{O}2\text{peak}}$. In the introductory phase of the program (Weeks 1-4), the frequency, duration, and intensity of aerobic training will be progressively increased from an initial prescription of 3 session/wk for ~30-60 mins/session at ~60-70% of $\text{v}_{\text{O}2\text{peak}}$ to the overall goal of this prescription 60%-100% $\text{v}_{\text{O}2\text{peak}}$ at the end of Week 4. In Weeks 5 to 8 (intermediate phase), the goal will be to introduce higher intensity aerobic training. Specifically, exercise intensity will range between ~60%-70% $\text{v}_{\text{O}2\text{peak}}$ for two sessions per week; in the remaining session, exercise intensity will be set at ventilatory

threshold (~75% $\text{v}_{\text{O}_2\text{peak}}$). In Weeks 9 to 16 (optimization phase), similar to the intermediate phase, participants will be asked to perform 3 aerobic sessions per week; 2 sessions will be performed at ~60%-80% $\text{v}_{\text{O}_2\text{peak}}$, and one interval workout. Interval workouts will consist of 1-2 min at the workload associated with $\text{v}_{\text{O}_2\text{peak}}$ (100% of $\text{v}_{\text{O}_2\text{peak}}$) followed by 2-4 min of active recovery for 8-12 or 4-6 intervals, depending on the length of the interval. At midpoint participants will undergo a CPET to re-assess $\text{v}_{\text{O}_2\text{peak}}$. On the basis of these results, the exercise prescription will be adjusted to ensure progressive improvements in $\text{v}_{\text{O}_2\text{peak}}$ across the entire intervention.

9.2.2 Arm B - Resistance Training

Resistance training will be prescribed with the aim of increasing $\text{v}_{\text{O}_2\text{peak}}$. The ultimate goal for resistance training alone is 3 resistance training sessions/week at an intensity above 50% to 85% of 1-RM for 30-60 minutes/session. Resistance training will be performed on stationary weight machines, modification in equipment may be made by Exercise Physiologist. Patients will be progressively trained to perform two to three sets of 75-85% of maximal strength.

9.2.3 Arm C - Combined Aerobic and Resistance Training

Combined aerobic and resistance training will be prescribed with the aim of increasing $\text{v}_{\text{O}_2\text{peak}}$. The ultimate goal will be three combined exercise sessions per week at an intensity above 50% $\text{v}_{\text{O}_2\text{peak}}$ and above 50% 1-RM for aerobic and resistance training, respectively for 30-90 minutes/session. In this arm, the duration of aerobic training and resistance training will not be added together but rather the exercise prescription is designed to exploit the complementary properties of aerobic and resistance training to optimally improve $\text{v}_{\text{O}_2\text{peak}}$. The prescription will be balanced to ensure that on days when aerobic training is prescribed at a high-intensity, resistance training (on the same day) will be conducted at a lower (easy) intensity and vice versa. This approach will optimize the desired adaptations without causing excessive fatigue and will help avoid potential interference effects between aerobic and resistance training.

9.2.4 Arm D - Progressive Stretching Group (Attention-Control)

The ultimate goal for the progressive stretching program is 3 individual stretching sessions (**see Appendix H**). All sessions are required to be supervised. Duration of the stretching sessions is prescribed and implemented in accordance with standard stretching and flexibility training principles. This approach will be applied to guide each participant's prescribed stretching plan, with dose and scheduling modifications made by exercise physiologists, as required.

9.3 Intervention Attendance and Adherence

Attendance is calculated as the number of intervention sessions attended divided by the total number of planned sessions (i.e., 3 times/wk x 16 weeks= 48). *Adherence* is defined as the number of scheduled training sessions attended, as well as whether the training session dose was

successfully completed (i.e., participant completed the intervention session at the planned duration and intensity) divided by the total number of planned sessions (i.e., 48).

9.4 Aerobic and Resistance Training Dose Modification

Vital signs will be monitored during intervention sessions to ensure participant safety. Vital sign changes that are outside the expected range of the intervention will be monitored by the exercise physiologist. The exercise physiologist will use clinical discretion to determine if a modification to the prescription or termination of the session is required.

All modifications will be source documented and recorded in the study database, including the modification reason, how the session was modified, and clearance obtained, as appropriate.

Participants requiring consistent modification of the planned prescription will be reviewed by the study PI and exercise physiologists to determine appropriate action (e.g., early study withdrawal, physiological re-evaluation).

Final determination of the intensity and duration of the session against the planned session goals will be conducted by the supervising exercise physiologist following the session and will be source documented.

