9.5 Aerobic Training /Resistance Training/ Progressive Stretching Discontinuation

Permanent treatment discontinuation is defined as cessation of aerobic training, resistance training or progressive stretching administration. When appropriate, follow up assessments will still be performed.

Temporary treatment interruption due to an adverse event is not considered permanent discontinuation. Patients whose treatment is interrupted due to an adverse event and then restarted will continue to have regularly scheduled study visits. In both experimental groups, the intensity and duration of the next scheduled session will be reviewed and discussed by ExOnc exercise personnel. However, if a participant misses more than 6 weeks of continuous sessions, the participant will begin the intervention from the starting prescription, due to the anticipated impact of deconditioning during the 6 weeks of intervention interruption.

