13.0 CRITERIA FOR REMOVAL FROM STUDY

The primary reasons for permanent treatment discontinuation are listed in **Table 4**.

Table 4. Primary Reasons for Permanent Treatment Discontinuation

Reason	Comment
Self-withdrawal (withdrawal of consent)	Patients may permanently discontinue study treatment and

	withdraw from the study at any time for any reason. Following study intervention discontinuation, patients should have protocol-required safety follow-up and long-term follow-up assessments unless the patient specifically declines further follow-up.
Adverse event or intercurrent illness or disease recurrence	Any intolerable adverse event (associated or not associated with the study intervention) that cannot be ameliorated by the use of adequate medical intervention or that, in the opinion of the principal investigator would lead to undue risk if study treatment were continued.
Gross noncompliance with protocol (violation)	The investigator may request permanent discontinuation of study treatment in the event of a major protocol deviation, lack of cooperation, or complete noncompliance.
Lost-to-follow-up	Reasonable effort should be made to contact any patient lost to follow-up during the course of the study in order to complete study-related assessments and record outstanding data.
Death	N/A

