14.0 BIOSTATISTICS

14.1 Sample Size Calculation and Justification

This randomized phase trial will accrue 67 subjects with lung cancer over an accrual period of ~36 months. The primary analysis will compare the efficacy of different types of exercise training modalities, relative to progressive stretching (attention control group), on $\text{v}_{\text{O}_2\text{peak}}$. Three separate t-tests will be used to compare each exercise training arm to the attention-control arm in mean change across time for $\text{v}_{\text{O}_2\text{peak}}$. The overall alpha level will be controlled at a two-sided 0.05 by using Holm's procedure.⁵⁶ That is, Holm's procedure first ranks the three p-values from lowest to highest. The first (lowest) p-value has to be less than 0.05/3 (0.0167) to be significant and permit continuation to the other t-tests. The Holm's procedure continues sequentially in this fashion using alpha levels of 0.05/2 (0.025) and 0.05/1 (0.05) for the remaining two t-tests, respectively. Power for this study is defined as the probability that at least one of the three t-tests of the arm effect on $\text{v}_{\text{O}_2\text{peak}}$ is significant; in other words, power is the probability that the first of the 3 ordered t-tests are significant. We assume that change in $\text{v}_{\text{O}_2\text{peak}}$ will have a standard deviation of $3.0 \text{ mL}\cdot\text{kg}^{-1}\text{min}^{-1}$. Statistical power depends upon the configuration of mean change in $\text{v}_{\text{O}_2\text{peak}}$ across the 4 arms. Thus, for example, 80% power is obtained when the mean change in $\text{v}_{\text{O}_2\text{peak}}$ across Arms A, B, C, and D is 0.60, 0.60, 2.10, and 0.0 ($\text{mL}\cdot\text{kg}^{-1}\text{min}^{-1}$), respectively.

A final important consideration when conducting exercise RCTs, is extent of exercise 'drop-in' or contamination in Arm D. In other words, the concern is that patients assigned to attention control independently initiate an exercise training program which, in turn, potentially dilutes the efficacy of aerobic training on the outcomes of interest. However, we feel this is less of a concern in the present study because patients (in the exercise training arms) will be provided with supervised, individualized training prescriptions (which will be difficult to replicate without sophisticated prescription algorithms and expertise) and attention-control participants are also provided with a supervised attention intervention.

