14.2 Primary and Secondary End Point Analyses

14.2.1 Primary End Point Analysis: The primary analysis will compare the efficacy of different types of exercise training modalities, relative to progressive stretching (attention control group), on $\text{v}_{\text{O}_2\text{peak}}$ in lung cancer.

An intent-to-treat statistical analysis will be conducted. Baseline characteristics will be compared using the Fisher exact test for categorical variables or a Wilcoxon rank sum test for continuous variables. The primary end point comparison will be analyzed using a multiple linear regression model to test for differences among and between the study arms in $\text{v}_{\text{O}_2\text{peak}}$ from baseline to follow up. The multiple linear regression model will include the baseline value of $\text{v}_{\text{O}_2\text{peak}}$, the stratification variables (i.e., chemotherapy treatment and sex), and study site.

In the absence of evidence to the contrary, multiple imputation strategies for missing Week 17 $\text{v}_{02\text{peak}}$ data will be performed assuming data were missing at random using linear regression. Results will be aggregated over 20 imputed sets using the variance formula by Rubin. In addition, a per-protocol analysis will be performed using a multiple linear regression model to test for differences among and between the study arms in $\text{v}_{02\text{peak}}$ from baseline to the post-intervention assessment (Week 17) on the basis of exercise attendance and adherence to the supervised exercise training in Arms A to C (<80% versus 80%).

14.2.2 Secondary End Point Analyses: As for the primary end point, the intention-to-treat principle will be employed for analysis of all secondary end points. Multiple linear regression models will be used to test for differences among and between the study arms in secondary end points from baseline to the postintervention assessment (Week 17). The multiple linear regression model will include the baseline value of $\text{v}_{02\text{peak}}$, the stratification variables (i.e., chemotherapy treatment and sex), and study site.

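### Stopping training is not kept apart from leaving the study, so Week 17 VO2peak may be lost in poor tolerators and imputed under missing-at-random without a sensitivity analysis, which may favour the exercise arms

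*Combined protocol and SAP*

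**What the plan says.** - **Section 9.4.** A participant whose prescription repeatedly needs changing is "reviewed by the study PI and exercise physiologists to determine appropriate action (e.g., early study withdrawal, physiological re-evaluation". Leaving the study is one of two examples. The heading limits the section to aerobic and resistance training, but the sentence itself speaks of participants generally. Section 9.2.4, on stretching, lets the physiologists adapt the plan and mentions neither a case review nor withdrawal.
- **Section 9.5, all arms, after permanent discontinuation.** "When appropriate, follow up assessments will still be performed". No criterion is given and nobody is named to decide.
- **Section 13.0, Table 4.** The section title concerns removal from the study, but the table lists reasons for stopping treatment. The self-withdrawal row says that "patients should have protocol-required safety follow-up and long-term follow-up assessments unless the patient specifically declines further follow-up". The lost-to-follow-up row asks for reasonable effort to reach patients so that assessments can be completed. The row for adverse events, illness and recurrence is silent on assessments, and so is the noncompliance row: "The investigator may request permanent discontinuation of study treatment in the event of a major protocol deviation, lack of cooperation, or complete noncompliance".
- **Table 1.** The Week 17 CPET is scheduled for all arms.
- **Section 14.1.** "Three separate t-tests will be used to compare each exercise training arm to the attention-control arm".
- **Section 14.2.1.** "An intent-to-treat statistical analysis will be conducted". Missing Week 17 VO2peak is multiply imputed, "assuming data were missing at random using linear regression. Results will be aggregated over 20 imputed sets". The only further analysis is per-protocol, by attendance and adherence below or above 80%.

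**The concern.** Section 9.4 ties possible exit from the study to something seen after randomization: how well the patient copes with the assigned training. The people who decide know that response, and the trial is open label. If such a patient leaves, or stops training and is not called back, the Week 17 CPET is lost for a reason that may be related to its value.

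The written route to study withdrawal sits in the section for the exercise modalities, so the loss may be heavier in Arms A to C than in Arm D. Imputation under missing-at-random then fills the gaps with values typical of tested patients who have the same covariates. If the untested patients would have done worse than that, the exercise arms look better than they are. No planned analysis would show it. The per-protocol analysis selects further on adherence, so it does not probe the assumption.

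**Working it through.** **1. The plan's own figures.** Section 16.02 reports 78 operable patients randomized at the first site, 70 completing and 8 lost. 70/78 = 89.7% and 8/78 = 10.3%; the printed 88% and 12% do not follow from these counts. I use 10.3%. It covers all causes and all four arms, without arm or reason, and no loss figure is given for the 15 inoperable patients. From Section 14.1 I use the SD of change (3.0 mL/kg/min) and the assumed mean changes (A 0.60, B 0.60, C 2.10, D 0.0). The stated 80% power does not enter. A simulation of the stated rule at 40 per arm gives 75.6%, which is a separate matter.

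**2. What each route says about the Week 17 CPET.**

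| Reason training ends | Text | Week 17 CPET required? |
|---|---|---|
| Repeated prescription changes | 9.4 | No; leaving the study is a named option |
| Any permanent discontinuation | 9.5 | Conditional, undefined |
| Self-withdrawal | Table 4 | Safety and long-term follow-up; CPET not named |
| Lost to follow-up | Table 4 | Effort to complete assessments |
| Adverse event, illness, recurrence | Table 4 | Silent |
| Noncompliance | Table 4 | Silent |

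**3. Formula.** Let m be the mean change in tested patients of an exercise arm, p the share selectively untested, and d their shortfall that the imputation model does not explain.

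- True arm mean: (1 − p)m + p(m − d) = m − pd.
- Arm mean after imputation under missing-at-random: m.
- Bias: pd.
- If Arm D loses a share p₀ with shortfall d₀, the net bias is pd − p₀d₀.

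**4. Numbers.** p and d are assumptions, and p₀d₀ is set to zero.

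| p | d | Bias (mL/kg/min) | Share of 2.10 (Arm C) | Share of 0.60 (Arms A, B) |
|---|---|---|---|---|
| 5% | 1 | 0.05 | 2% | 8% |
| 10.3% | 2.1 | 0.22 | 10% | 36% |
| 10% | 3 | 0.30 | 14% | 50% |
| 15% | 3 | 0.45 | 21% | 75% |

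**5. Check through the planned imputation.** I simulated four arms of 40, a true intent-to-treat effect of zero, selective loss in Arms A to C only, 20 imputed sets, baseline and arm in the model, and the first Holm step at 0.05/3, with 4,000 trials per setting.

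| Loss | Shortfall | Mean bias | p × d | Family-wise error |
|---|---|---|---|---|
| about 0 | – | 0.01 | 0 | 4.9% |
| 10.3% | 2.1 | 0.23 | 0.22 | 6.3% |
| 10.3% | 3.0 | 0.31 | 0.31 | 7.9% |
| 20% | 2.1 | 0.42 | 0.42 | 9.4% |
| 20% | 3.0 | 0.59 | 0.60 | 15.4% |

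The formula holds under multiple imputation. The 20% rows are a stress case outside the assumed range.

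**The case against.** A reader might infer that poor tolerators drop out of the primary analysis, and that this contradicts the intent-to-treat statement. The documents do not support that. Section 14.2.1 keeps these patients in the analysis by imputation, so the open question is whether the missing-at-random assumption holds. The plan also makes that assumption a default, to be used unless evidence points the other way. It does not say what evidence would count or what would then be done.

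A reader might also infer that the protocol requires such patients to be removed, or that only the self-withdrawal row protects follow-up. Withdrawal is one example after a case review, beside re-evaluation. The lost-to-follow-up row also seeks assessments. The noncompliance row concerns treatment, not participation, and Section 9.5 leans towards assessing.

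Other points carry weight:

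- The difference between arms rests largely on the heading of Section 9.4. Sections 9.5 and 13.0 apply to all arms, and illness or progression may remove declining patients from Arm D too, which would offset the bias.
- The per-protocol split at 80% presupposes Week 17 data in low adherers. At the first site, mean adherence in Arms A to C was 77%, yet 70 of 78 operable patients completed. This suggests that imperfect adherers were tested, although an average cannot prove it.
- A p of 10% assigns to selective loss about the whole observed all-cause rate, and a d of 3 is a full SD of change. Any part of d explained by the imputation predictors, which the plan does not list, drops out of the bias.

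These points limit the size and the certainty. They do not close the gap: nowhere is the Week 17 CPET sought regardless of training status, and nothing tests the imputation assumption.

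**Conclusion.** The concern holds in a limited form. The text allows the primary outcome to be lost in relation to tolerance of training, and the planned imputation would not correct for that if untested patients do worse than tested patients with the same covariates. The comparison may then favour the exercise arms.

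Under the assumed ranges the bias is 0.05 to 0.45 mL/kg/min. The upper end is an extreme case, because it needs selective loss above the 10.3% all-cause loss in operable first-site patients, a shortfall of one SD, and no offset in Arm D. That cohort may not represent the wider population now eligible, so the range could be wrong in either direction. How often staff would withdraw patients, and in which arms, cannot be known from the documents. This is worth correcting because a missing test cannot be recovered at the analysis stage, but it does not show that the trial's result would be biased.

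**What to change.** 1. Reconcile Sections 9.4, 9.5 and 13.0 (Table 4) so that stopping the intervention and leaving the study are separate events. Section 9.4 need only say that a decision about training does not by itself end study assessments.
2. Replace the open qualifier in Section 9.5 with a rule: the Week 17 CPET and other assessments are sought from every randomized patient whatever their training status, unless the patient has died, withdraws consent for assessments, or has a contraindication to testing. Apply it to the adverse event/recurrence and noncompliance rows of Table 4.
3. In Section 14.2.1, add a sensitivity analysis for missing Week 17 VO2peak. It could be delta-adjusted (imputed values in Arms A to C lowered over a range, for example 0 to 3.0 mL/kg/min, showing where each conclusion changes) or reference-based (missing exercise-arm values imputed from Arm D).

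Decisions on when or why training is modified or stopped stay exactly as they are.

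The cost is wording in three protocol sections, some effort to bring back patients who no longer train, and a little more analysis. Table 1 already schedules the visit. The first two changes can help only the 67 patients recruited at the second site, because the 93 at the first site were already randomized; the third covers all 160.
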